10.1. Potential Risks

Medtronic follows rigorous Quality Assurance and Control procedures throughout the life of a product, from the business analysis phase through development, market release, and post-market surveillance.

VP and BKP are not investigational procedures and the risk associated with VP or BKP procedures are the same as for the one performed per clinical practice.

VP And BKP are the two procedures that will be used in both the investigational group (Xpede group) and the control group (Mendec) and the randomization will be stratified by the procedures. Hence the focus of risk and benefit analysis should be purely on the usage of Xpede versus Mendec

Serious adverse events, some with fatal outcome, associated with the use of acrylic bone cements as specified in the IFU include:

- cardiac arrest
- cerebrovascular accident
- myocardial infarction
- pulmonary embolism

Other reported adverse events relevant to the anatomy being treated with acrylic bone cements include:

- deep or superficial wound infection
- fistula
- hematoma
- hemorrhage
- heterotopic new bone formation
- extravasation of bone cement potentially resulting in but not limited to:
- compression or irritation of nerve structures, such as the spinal cord or nerve roots, causing radiculopathy, paresthesia, paraplegia or paralysis and/or;
- introduction into the vascular system resulting in embolism of the lung and/or heart or other

Medtronic Confidential

clinical sequelae

- pyrexia due to allergy to bone cement
- short-term conduction irregularities
- thrombophlebitis
- transitory fall in blood pressure
- migration of hardened bone cement bolus

10.2. Potential Benefits

The potential benefits of the KYPHON® Xpede™ Bone Cement are consistent with the vertebral body fracture therapy provided by similar currently approved Bone Cement.

Possible benefits of the use of bone cement include vertebral body height restoration, angular deformity correction, vertebral body volume increase, reduction in back pain, reduction in the number of days per month that the subject remains in bed, improvement in quality of life, improvement in ability to perform activities of daily living, subject satisfaction with the procedure, improvement in pain and mobility.

The information gained from this study could result in the improved management of patients suffering from Vertebral body fracture. Additionally, information collected from this study may assist in the design of new product(s)/therapy(ies) and/or instructions for use.

10.3. Risk-Benefit Rationale

KYPHON® Xpede™ Bone Cement had already been approved and widely used in different regions around the world, including EU and USA.

Risks associated with using the KYPHON® Xpede™ Bone Cement are similar to those associated with any other approved bone cement used during VP, BKP procedures.

For control arm Mendec Spine, it is a NMPA approved product. So the risks are also similar to using any other approved Bone Cement.

Compared with eligible patients who receive routine hospital care (any approved DES) and do not participate in this study, subjects will have very limited extra risks than using any approved DES.

Based on post market risk analysis and on the published scientific literature on equivalent products that are currently on the market and indicated for the same intended use as the KYPHON® Xpede™

Bone Cement, we anticipate that the benefits of using the KYPHON® Xpede™ Bone Cement outweigh the risks associated with the use of this product.

10.4. Probability analysis of success

The manufacturing system of Medtronic has been tested and proven for many years. The quality of the investigational device has been carefully examined and verified before delivery. The investigational device has been commercially available globally, including the Europe and many other countries. The basic principles, structure composition and materials etc. either comply with the international and domestic standards, or have been carefully examined and verified by Medtronic, as well as tested, qualified by NMPA certificated medical device testing organization. The study design of this study complies with related NMPA instructions and requirements of ethical review, and all potential subjects will be strictly selected according to indications of the investigational device.

10.5. Probability analysis of failure

Although regulatory, ethical, scientific and medical requirements have been fully taken into consideration, the unanticipated risk in the clinical application of investigational device could lead to failure of this study. Potential risks could be reduced with well-trained study staff and strict protocol compliance.

11. Adverse Events and Device Deficiencies

11.1. Definitions/Classifications

Table 6: Adverse Event Definitions

Event Type	Definition
Adverse Event (AE)	
Any untoward medical occurrence, unintended disease or injury, or untoward clinical signs (including abnormal laboratory findings) in subjects, users or other persons, whether or not related to the investigational medical device.
 
NOTE 1: This definition includes events related to the investigational medical device or the comparator.
 
NOTE 2: This definition includes events related to the procedures involved.
 
NOTE 3: For users or other persons, this definition is restricted to events related to investigational medical devices.

Xpede Clinical Investigation Plan

Event Type	Definition
	
(ISO 14155:2011⁹ section 3.2)
 
The medical events with disadvantages occurred during the clinical study, no matter whether they are related to investigational medical devices or not.
 
(CFDA Order No. 25 Article 93)

Serious Adverse Event (SAE)	
Adverse event that
 
a) led to death,b) led to serious deterioration in the health of the subject, that either resulted in
1) a life-threatening illness or injury, or2) a permanent impairment of a body structure or a body function, or3) in-patient or prolonged hospitalization, or4) medical or surgical intervention to prevent life-threatening illness or injury or permanent impairment to a body structure or a body function,c) led to fetal distress, fetal death or a congenital abnormality or birth defect. 
NOTE: Planned hospitalization for a pre-existing condition, or a procedure required by the CIP, without serious deterioration in health, is not considered a serious adverse event.
 
(ISO 14155:2011 section 3.37)
 
Any untoward medical occurrence during the clinical study: results in death or serious deterioration in health; life-threatening diseases or injuries; causing permanent damage to the body structure or function; requires hospitalization or prolongation of hospitalization; requires medical operations or intervention for preventing from persistent or significant disability/incapacity; results in fetal distress, fetal death, or congenital anomaly/birth defect.
 
(CFDA Order No. 25 Article 93)

Adverse Device Effect (ADE)	
Adverse event related to the use of an investigational medical device.
 
NOTE 1: This definition includes adverse events resulting from insufficient or inadequate instructions for use, deployment, implantation, installation, or operation, or any malfunction of the investigational medical device.
 
NOTE 2: This definition includes any event resulting from use error or from intentional misuse of the investigational medical device.
 
(ISO 14155:2011 section 3.1)

Serious Adverse Device Effect (SADE)	
Adverse device effect that has resulted in any of the consequences characteristic of a serious adverse event.
 
(ISO 14155:2011 section 3.36)

⁹ International Standard ISO 14155:2011(E). Clinical investigation of medical devices for human subjects – Good Clinical Practice.

Event Type	Definition
Unanticipated Serious Adverse Device Effect (USADE)	
Serious adverse device effect which by its nature, incidence, severity or outcome has not been identified in the current version of the risk analysis report.
 
NOTE: Anticipated serious adverse device effect (ASADE) is an effect, which by its nature, incidence, severity or outcome has been identified in the risk analysis report.
 
(ISO 14155:2011 section 3.42)

Device Deficiency(DD)	
Inadequacy of a medical device with respect to its identity, quality, durability, reliability, safety or performance.
 
NOTE: Device deficiencies include malfunctions, use errors, and inadequate labeling.
 
(ISO 14155:2011 section 3.15)
 
Any unreasonable risk caused by a medical device in normal use during clinical study that may endanger human health or life safety, such as label error, quality issues, malfunction and etc.
 
(CFDA Order No. 25 Article 93)

Adverse Event Relationship Classification

Causality assessments define the relationship between the use of the medical device (including the medical-surgical procedure) and the occurrence of each adverse event. During causality assessment activity, clinical judgment shall be used and the relevant documents, such as the Clinical Evaluation Report and the Risk Management Report shall be consulted, as all the foreseeable serious adverse events and the potential risks are listed and assessed there. The presence of confounding factors, such as concomitant medication/treatment, the natural history of the underlying disease, other concurrent illness or risk factors shall also be considered.

The sponsor and the investigators will use the following definitions to assess the relationship of the adverse event to the investigational medical device (or comparator) or procedures.

1) Not related: relationship to the device or procedures can be excluded when:

- the event is not a known side effect of the product category the device belongs to or of similar devices and procedures;
- the event has no temporal relationship with the use of the investigational device or the procedures;
- the event does not follow a known response pattern to the medical device (if the response pattern is previously known) and is biologically implausible;
- the discontinuation of medical device application or the reduction of the level of activation/exposure - when clinically feasible - and reintroduction of its use (or increase of the level of activation/exposure), do not impact on the serious event;

- the event involves a body-site or an organ not expected to be affected by the device or procedure;
- the event can be attributed to another cause (e.g. an underlying or concurrent illness/ clinical condition, an effect of another device, drug, treatment or other risk factors);
- the event does not depend on a false result given by the investigational device used for diagnosis, when applicable;
- harms to the subject are not clearly due to use error;
- In order to establish the non-relatedness, not all the criteria listed above might be met at the same time, depending on the type of device/procedures and the event.

2) Unlikely: the relationship with the use of the device seems not relevant and/or the event can be reasonably explained by another cause, but additional information may be obtained.

3) Possible: the relationship with the use of the investigational device is weak but cannot be ruled out completely. Alternative causes are also possible (e.g. an underlying or concurrent illness/ clinical condition or/and an effect of another device, drug or treatment). Cases where relatedness cannot be assessed or no information has been obtained should also be classified as possible.

4) Probable: the relationship with the use of the investigational device seems relevant and/or the event cannot reasonably be explained by another cause, but additional information may be obtained.

5) Causal relationship: the serious event is associated with the investigational device or with procedures beyond reasonable doubt when:

- the event is a known side effect of the product category the device belongs to or of similar devices and procedures;
- the event has a temporal relationship with investigational device use/application or procedures;
- the event involves a body-site or organ that
 - o the investigational device or procedures are applied to;
 - o the investigational device or procedures have an effect on;
- the serious event follows a known response pattern to the medical device (if the response pattern is previously known);
- the discontinuation of medical device application (or reduction of the level of activation/exposure) and reintroduction of its use (or increase of the level of activation/exposure), impact on the serious event (when clinically feasible);
- other possible causes (e.g. an underlying or concurrent illness/ clinical condition or/and an effect of another device, drug or treatment) have been adequately ruled out;
- harm to the subject is due to error in use;

- the event depends on a false result given by the investigational device used for diagnosis, when applicable;
- In order to establish the relatedness, not all the criteria listed above might be met at the same time, depending on the type of device/procedures and the event.

The sponsor and the investigators will distinguish between the adverse events related to the device and those related to the procedures (any procedure specific to the clinical investigation). An adverse event can be related both to procedures and the device. Complications of procedures are considered not related if the said procedures would have been applied to the patients also in the absence of device use/application.

In some particular cases the event may be not adequately assessed because information is insufficient or contradictory and/or the data cannot be verified or supplemented. The sponsor and the Investigators will make the maximum effort to define and categorize the event and avoid these situations. Where the sponsor remains uncertain about classifying the event, it should not exclude the relatedness and classify the event as "possible".

Unavoidable Adverse Event Related to the Procedure: An Adverse Event inherent to a surgical procedure that is expected to occur in all subjects for a projected duration including but not limited to the one listed in Table 7.

Table 7: Unavoidable Adverse Events

Event Description	Time Frame (hrs) from end of Procedure
Anesthesia related nausea / vomiting	24 hrs
Low-grade fever (<100°F or < 37.8°C)	48 hrs
Mild to moderate bruising / ecchymosis	168 hrs (7 days)
Sleep problems (insomnia)	72 hrs

Unavoidable events shall not be reported as AE unless the adverse event worsens or is present outside the stated timeframe.

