9.1. Schedule of Events

Table 5: Schedule of Events

Data to be collected	& Baseline Randomization	Study Procedure (Day 0)	Post 1 day Operative	3 months post op	6 months post op	Unscheduled
Visit windows		Can be performed the same day of baseline	(After 24 hours but not later than 1 week)	±2 weeks	±2 weeks	NA
Inclusion/Exclusion criteria	X					
Informed Consent Form ³	X					
Demographics and medical history	X					

³To be obtained before any study related procedure

Physical examination	X					
MRI	X					
Study Procedure Data		X				
Concomitant specific medication	X		X	X	X	X
NRS score	X		X	X	X	X
ODI	X		X	X	X	X
AP/Lateral X-ray	X		X	X	X	X
SF36	X		X	X	X	X
Device disposition		X				
Adverse events review (subject and non-subject) and death information	Upon Occurrence					
Device Deficiency review	Upon Occurrence					
Protocol deviation review	Upon Occurrence					
Reason for premature study termination	Upon Occurrence					

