9.10. Assessment of Safety

Timely, accurate, and complete reporting and analysis of safety information is crucial for the protection of subjects, clinicians, and the sponsor. Reporting and analysis of safety data are mandated by regulatory authorities worldwide. Medtronic has established Standard Operating Procedures (SOPs) to ensure compliance with global regulatory safety reporting requirements. Study activities are conducted in accordance with these SOPs.

All adverse events are collected throughout the duration of this study, starting from the time of signing the ICF through study closure. Adverse Events are to be reported upon site awareness using an adverse event CRF, capturing date of the event; date site became aware of the event, diagnosis of the event, actions taken, assessment of seriousness, relatedness and outcome.

Unavoidable Adverse Events (refer to Table 7) need not be reported unless the adverse event worsens or is present outside the stated timeframe.

Adverse Events will be recorded and reported according to local regulatory requirements and are outlined in Table 8. It is the responsibility of the Investigator to abide by the adverse event reporting requirements stipulated by local law and the sites' Ethics Committee.

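### The exemption for unavoidable adverse events is open-ended and conflicts with the protocol and SAP statements that all adverse events are collected

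*Protocol*

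**What the plan says.** Protocol section 9.10 opens with a general rule: "All adverse events are collected throughout the duration of this study, starting from the time of signing the ICF through study closure". It then makes an exception: "Unavoidable Adverse Events (refer to Table 7) need not be reported unless the adverse event worsens or is present outside the stated timeframe".

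Section 11.1 words the exception differently. An unavoidable event must belong to the operation itself, and it is further described as one "that is expected to occur in all subjects for a projected duration including but not limited to the one listed in Table 7". Under Table 7 it adds: "Unavoidable events shall not be reported as AE unless the adverse event worsens or is present outside the stated timeframe".

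Table 7 has four entries, each with a limit counted from the end of the procedure: anesthesia-related nausea or vomiting (24 h), low-grade fever below 37.8°C (48 h), insomnia (72 h), and mild to moderate bruising (168 h).

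Section 11.2 requires investigators to evaluate and document all adverse events from consent onward, and Table 8 repeats the duty to record them all. SAP section 7.10 also says all adverse events are collected. It plans Table 3.1.2 (by system organ class and preferred term), Table 3.1.3 (adding relationship to bone cement) and Listing 2, and does not mention the exemption.

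Among the cement risks, section 10.1 lists "pyrexia due to allergy to bone cement".

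**The concern.** Adverse events through 6 months are a secondary endpoint and the main safety evidence in a registration trial. A rule that keeps events off the adverse event form should be closed, stated the same way throughout, and visible in the analysis plan. This one is none of these.

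A site reading section 11.1 may not report a Table 7 event and may extend the category to events not in the table. A site reading section 9.10 may choose whether to report a Table 7 event and has no licence to go beyond the table. A site reading section 11.2 must document everything. Event counts could then differ by site for reasons unrelated to the cement, and a reader of the SAP tables would not know that anything had been left out.

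The exempted period is also when an acute reaction to cement would be looked for. Both products are PMMA, but protocol Table 2 shows that Xpede has less benzoyl peroxide than Mendec (0.9% against 2.5%) and less N,N-dimethyl-p-toluidine (0.6% against 0.9%). Early reactions are a fair question for this comparison.

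**Working it through.** The plan states no adverse event rate and no safety margin, so there is no figure to reproduce. The check sets the sections side by side and then compares the time limits with the visit schedule.

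**1. The four statements**

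| Place | Scope of the exemption | Force |
|---|---|---|
| Protocol 9.10 | Table 7 | Need not be reported |
| Protocol 11.1 | Table 7 and unspecified others | Shall not be reported |
| Protocol 11.2 | None | All must be documented |
| SAP 7.10 | None | All are collected |

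Scope and force both differ, and two of the four places have no exemption.

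**2. What brings an event back**

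There are two triggers: worsening, or presence beyond the stated time. For a Table 7 event both can operate. For an unlisted event no time is stated, so the second cannot operate and only worsening remains.

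**3. What limits the open list**

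The definition has three conditions: inherent to a surgical procedure, expected in all subjects, and of projected duration. The second looks restrictive. But Table 7's own entries include vomiting, low-grade fever and insomnia, which are not plausibly universal. If those qualify, the condition gives a site no usable test for what else does.

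**4. Overlap with cement risks**

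The nausea entry is qualified by cause ("Anesthesia related nausea / vomiting"). The fever entry is qualified only by temperature and time. A low-grade fever in the first 48 hours could be an allergic reaction of the kind named in section 10.1 and still meet the entry. Section 11.1 says that uncertain cases should be classed as possibly related, but that rule acts on events that are assessed. An event not reported as an adverse event does not reach SAP Table 3.1.3.

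**5. Can scheduled visits check the limits?**

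The early visit window in protocol Table 5 is "After 24 hours but not later than 1 week", that is, 24 to 168 h. The share of the window at or after a limit L is (168 − L) / (168 − 24):

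- Nausea or vomiting, 24 h: 144/144 = 100%
- Low-grade fever, 48 h: 120/144 = 83%
- Insomnia, 72 h: 96/144 = 67%
- Bruising, 168 h: 0/144 = 0%

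An on-time visit can check the first limit whenever it is held and the next two if it is held late enough. It can never show bruising lasting beyond 168 h. The next scheduled visit is at 3 months ±2 weeks; with the SAP 7.12 target of Day 90, the earliest is Day 90 − 14 = Day 76.

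**6. Blinding**

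Sections 9.8 and 9.9 specify blinded assessment for imaging and efficacy. Section 9.7 has the investigator or a delegated nurse or coordinator collect adverse events and does not mention blinding. No independent event review is specified.

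**The case against.** The best reply is that this is a wording matter about trivial events. Worsening keeps any event reportable. Fever at or above 37.8°C, or beyond 48 h, is reportable. Bone cement implantation syndrome, leakage and fractures are named for reporting in section 5.2.2, extravasation is collected as procedure data under section 9.6, and serious events have their own route in Table 8. All of this stands, and it limits the likely damage to minor early events. It does not settle which of the conflicting rules a site should follow, or tell a reader of the SAP tables that events were withheld.

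A reader might infer several stronger points that the documents do not support:

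- **Unblinded operators apply the exemption.** No section says who applies it or whether that person is blinded. The documents are silent, which is a gap but not evidence of unblinded filtering.
- **Hematoma, a transient fall in blood pressure or conduction irregularities can be dropped.** Section 10.1 lists these as risks, and nothing suggests that they are expected in all subjects, so they do not plainly meet the definition.
- **Unlisted events can never be reported.** Worsening still brings them back.
- **The visit schedule cannot check the time limits.** This is strictly true only for bruising at 168 h. Table 5 also sets adverse event review upon occurrence, so detection does not depend on visits alone.
- **The exemption creates a false difference between arms.** Any figure would need assumed event rates and assumed unequal filtering, and so would assume its own result.

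**Conclusion.** The point holds as a defect of specification. Section 11.1 bars reporting of an open-ended class of events, gives the unlisted ones no time limit, and conflicts with sections 9.10 and 11.2 and SAP section 7.10. Some events would miss causality assessment and the table by relationship to bone cement, and low-grade fever within 48 hours is the clearest case.

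The effect falls on the secondary adverse event endpoint and the safety tables. Its size cannot be estimated from the documents. Because blinding is not stated for adverse event assessment, unequal filtering between arms is possible, but nothing shows that it would occur.

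The conclusion rests on the current wording of the four sections and on one judgement: that Table 7's entries are not truly expected in every subject. It should be corrected, because the core change is nearly free.

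**What to change.** **Core change.** In protocol section 11.1, replace the open-ended reference with wording that limits unavoidable events to those listed in Table 7. Reconcile sections 9.10, 11.1 and 11.2 (with Table 8) and SAP section 7.10, so that each states the same scope and the same force. This costs a few sentences.

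**Preferred addition.** Record Table 7 events in both arms with an expected-event flag and the date and time of onset and resolution. Clock times are needed because the limits are in hours from the end of the procedure and dates alone cannot resolve them. For the same reason the end-of-procedure time should be captured; section 9.6 lists the duration of the procedure but not its end time. Apply the 24, 48, 72 and 168 h limits when adverse events are tabulated, show flagged events by arm in a separate table, and state the rule in SAP section 7.10. Low-grade fever then needs no separate treatment, because it would be recorded with the rest.

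The addition costs one form flag, the time fields, one table and some more minor entries for sites.
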